5.2.1 Hematologic toxicity

The standard NCI Common Terminology Criteria for Adverse Events (CTCAE) v.5.0 criteria will be replaced by these criteria:

- Any Grade 4 event, including laboratory electrolyte abnormalities, that is not easily reversed without sequelae
- Grade 4 neutropenia (Absolute Neutrophil Count (ANC) $<0.5 \times 10^9/L$)
- Grade 3 febrile neutropenia (ANC $<1.0 \times 10^9/L$ with a fever $\geq 38.3^{\circ}C$)
- Grade 4 thrombocytopenia ($<25.0 \times 10^9/L$) lasting >4 days or that requires platelet transfusion
- Grade ≥ 3 thrombocytopenia ($<50.0-25.0 \times 10^9/L$) associated with Grade ≥ 3 bleeding
- Grade 2 concurrent AST or ALT $>3\times$ ULN and total bilirubin $>2\times$ ULN without evidence of cholestasis
- Any toxicity resulting in death (*i.e.*, Grade 5)

Note: Peripheral lymphocytopenia after the first CYT107 injection is not a sign of toxicity; it reflects the lymphocytes “homing effect” of *rhIL-7*. Lymphocyte counts usually come back to baseline 5 to 7 days after the first injection.

5.2.2 Non-hematologic toxicity

Any Grade ≥ 3 non-hematologic toxicity (CTCAE v5.0), ***except*** for the following, which will not constitute DLTs:

- Grade ≥ 3 nausea or vomiting lasting ≤ 72 hours with the use of adequate/maximal medical intervention and/or prophylaxis

- Grade 3 diarrhea lasting \leq 72 hours with the use of adequate/maximal medical intervention and/or prophylaxis
- Grade 3 fatigue lasting \leq 7 days
- Grade 3 injection site reaction (unless operative intervention is required)
- Grade 3 hyperglycemia lasting \leq 72 hours with standard antidiabetic therapy
- Grade 3 increases in liver transaminases ($>5.0-20.0 \times$ ULN) in patient with liver metastases
- Clinical laboratory abnormalities that are reversible to \leq Grade 1 or baseline status within 72 hours with outpatient care and/or monitoring, or that are considered not clinically significant by the treating physician

Management and dose modifications associated with the above AEs are outlined in [Section 6](#).

The AEs will be assessed by the Toxicity Evaluation Committee, which includes the PI(s), study sponsor(s), CTEP and the CITN Central Operating and Statistical Center (COSC).

The patients must complete the full 4-week DLT window to be considered evaluable for DLTs. Patients who discontinue from the study before completion of the full 4-week DLT window for reasons other than the occurrence of a DLT (e.g., withdrawal of consent, rapid tumor progression, death due to rapid tumor progression, AE that does not meet DLT criteria) will not be considered evaluable for DLTs and will be replaced.

All randomly assigned patients will be monitored for occurrence of DLT. Monitoring of all safety and toxicity data is done by the PI, the study Sponsor(s) and the CITN COSC on a real-time basis as data are entered into Medidata Rave using the Web Reporting Module. All participating sites must notify the PI and CITN COSC when a DLT has occurred.

A delay due to toxicity in receiving the second cycle of therapy of >14 days will be considered a DLT in subjects enrolled in the safety run-in phase of the study. This does not apply to subsequent subjects enrolled in the randomized component of the study.

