5. TREATMENT PLAN

This is a phase II trial of atezolizumab (MPDL3280A) plus recombinant human IL-7 (CYT107) in patients with locally advanced or metastatic urothelial carcinoma. The trial follows a randomized, controlled trial design, with an initial 'Safety Run-In' phase designed to evaluate the acute safety profile of the investigational treatment combination.

During the Safety Run-In phase, 6 patients will be assigned to the experimental arm (atezolizumab + CYT107) with staggered enrollment. This will be accomplished with an initial 3 patient enrollment. All adverse events will be assessed by the Toxicity Evaluation Committee. If 0-1 patient experiences a protocol-defined DLT (refer to [Section 5.2](#)) after completion of the 4-week DLT window, an additional 3 patients will be enrolled. Once all 6 patients have completed the 4-week DLT window, the Toxicity Evaluation Committee will again assess all adverse events. If, at any time, 2 or more patients experience a protocol-defined DLT, further enrollment into the trial will be suspended.

If the treatment combination of the experimental arm demonstrates an acceptable safety profile in the Safety Run-In (one or fewer patient experiences a protocol-defined DLT), randomized enrollment into the trial will begin.

Patients will be randomly assigned to either the control arm (atezolizumab monotherapy) or experimental arm (atezolizumab + CYT107) of the trial.

The first 6 subjects enrolled in the run-in phase of the study will have PK sampling done at baseline (prior to CYT107 administration), and at week 4 prior to CYT107 administration and at 2 hours, 4 hours and 6 hours after the fourth CYT107 administration.

Anti-drug antibody testing (ADA testing) will be done on all subjects who receive CYT107. Testing will be done at baseline (prior to CYT107 administration) and at week 8, (1 month after

the last CYT107 administration.) Any subject who develops binding antibodies will be further tested for the presence of anti-CYT107 neutralizing antibodies.

Randomization in the OPEN system may be performed up to 5 business days before initiation of study treatment to allow for clinical site logistics.

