5.1 Agent Administration

Reported adverse events and potential risks are described in [Section 7](#). Appropriate dose modifications are described in [Section 6](#). No investigational or commercial agents or therapies other than those described below may be administered with the intent to treat the patient's malignancy.

Regimen Description					
EXPERIMENTAL ARM					
Agent	Premedications; Precautions	Dose	Route	Schedule	Cycle Length
Atezolizumab	antihistamines or antipyretics/ analgesics ¹	1200 mg	IV	Day 8 of Cycle 1 (28-day cycle) and Day 1 of Cycle 2+ (21-day cycles)	Cycle 1: 28 days Cycle 2+: 21 days
IL-7 (CYT107)²	None	10 mcg/kg	IM	Days 1, 8, 15 and 22 of Cycle 1 only	
CONTROL ARM					
Atezolizumab	antihistamines or antipyretics/ analgesics ¹	1200 mg	IV	Day 1 of each cycle	21 days

Note: ¹Premedication *not* permitted for the first dose on either arm; ²Calculate the required dose amount (10 mcg/kg) based on patient's baseline weight. The dose amount should be recalculated if the patient's weight changes by more than 10% from the baseline weight measurement.

5.1.1 *Atezolizumab*

All patients enrolled into this study will receive atezolizumab. Atezolizumab will be administered on Day 1 of each 21-day cycle in the control arm. Atezolizumab will be administered on Day 8 of Cycle 1 (28-day cycle) and on Day 1 of each subsequent cycle (21-day cycle) on the experimental arm. Atezolizumab may be administered up to 2 days before or after the scheduled administration date of each cycle due to administrative reasons.

Administration of atezolizumab will be performed in a setting with emergency medical facilities and staff who are trained to monitor for and respond to medical emergencies.

Atezolizumab will be administered following the CYT107 injection on Day 8 of Cycle 1 for patients enrolled in the Safety Run-in Phase and experimental arm.

For anaphylaxis precautions, see the management guidelines below. Atezolizumab infusions will be administered per the instructions outlined in the Table below.

First Infusion	Subsequent Infusions

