5.1.4 Other procedures: Microbiome Sample Collection

Pre-treatment and post-treatment microbiome samples will be collected by patients using standard, at home stool-collection procedures using standardized fecal swab/storage devices. The samples will be stored frozen at home by patient and returned to the clinical research site at their next study visit.

Patients will be provided with fecal swab/storage devices and instructions (refer to [Appendix E](#)) at the screening visit and at the Cycle 3, Day 1 visit.

5.2 **Safety Run-in: Definition of Dose-Limiting Toxicity**

Dose-limiting toxicity is defined as any adverse event (AE) occurring within the first 28 days (*i.e.*, from Week 1 Day 1 through Week 4 Day 7), that is considered to be ***at least possibly related*** to the protocol treatment (atezolizumab, CYT107 or both), and that meets at least one of the non-hematologic or hematologic criteria below:

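### A Cycle 2 toxicity delay of more than 14 days is a run-in DLT first established about day 44, but both go/no-go decisions may be taken at day 28, so a hold open at the decision can leave the DLT count incomplete

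*Combined protocol and SAP*

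**What the plan says.** **Definition.** Section 5.2 sets the window: "Dose-limiting toxicity is defined as any adverse event (AE) occurring within the first 28 days", running to Week 4 Day 7. The last paragraph of Section 5.2.2 then adds a criterion of another kind: "A delay due to toxicity in receiving the second cycle of therapy of >14 days will be considered a DLT". It is confined to the run-in: "This does not apply to subsequent subjects enrolled in the randomized component of the study".

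**Decisions.** Section 5 (Treatment Plan) enrolls three patients first. If none or one has a DLT "after completion of the 4-week DLT window, an additional 3 patients will be enrolled". The second review is timed the same way: "Once all 6 patients have completed the 4-week DLT window, the Toxicity Evaluation Committee will again assess all adverse events". Randomization opens if at most one of the six has a DLT. Sections 5 and 13.3 also suspend enrollment whenever two or more patients have had a DLT.

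**Evaluability.** Sections 5.2.2, 5.7 and 13.3 call a patient evaluable for DLTs after completing four weeks (28 days).

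**Schedule.** Section 5.1.1 gives the experimental-arm regimen, which run-in patients follow: "Atezolizumab will be administered on Day 8 of Cycle 1 (28-day cycle) and on Day 1 of each subsequent cycle (21-day cycle"). Dosing has some latitude: "Atezolizumab may be administered up to 2 days before or after the scheduled administration date of each cycle due to administrative reasons".

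**The concern.** The definition, the evaluability rule and both decision times are all set at 28 days, but one DLT criterion can only be met later. No section extends the window, the evaluability rule or the committee review to cover it. If a patient's Cycle 2 is being held for toxicity when the decision is taken, that patient can be counted as free of DLT and become a DLT about two weeks later under the protocol's own wording.

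This matters because the pass rule has no slack. With one DLT already counted among the six, one pending event separates opening randomization from suspending the trial. With one counted among the first three, it separates enrolling the second cohort from suspension. The patients put at risk are those enrolled to a new combination in the interval.

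The two texts also leave it arguable whether a delay established on day 44 is a protocol-defined DLT at all, since Section 5.2 stops at day 28. That uncertainty reaches the suspension rule and the reported run-in DLT count.

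**Working it through.** **The plan's own figure.** Section 13.2 gives 16.7% as the highest acceptable DLT incidence in six patients. 1/6 = 16.7%, so it reproduces. The next possible count is 2/6 = 33.3%, which triggers suspension.

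**When the delay criterion can be met** (Sections 5.1.1 and 5.2.2):
- Cycle 1 lasts 28 days, so Cycle 2 Day 1 = 1 + 28 = day 29.
- Exactly 14 days late = 29 + 14 = day 43.
- First day more than 14 days late = 29 + 15 = day 44.
- Counted from the edges of the ±2-day window: 27 + 15 = day 42, and 31 + 15 = day 46.
- Gap after the window closes: 44 − 28 = 16 days (range 42 − 28 = 14 to 46 − 28 = 18).

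**When it is settled without a delay.** A patient who receives Cycle 2 on schedule is resolved for this criterion on about day 29 (day 27 to 31). The count therefore stays open toward day 44 only when Cycle 2 is not given on time because of toxicity.

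**Whether the criterion catches anything the others miss.** Section 5.2.2 generally requires Grade 3 or higher for a non-hematologic DLT. Section 6.1.2 withholds atezolizumab and starts corticosteroids for Grade 2 pulmonary and renal events, and for Grade 2 hepatic events lasting more than 5 days. It requires a taper of at least one month before atezolizumab resumes. Taking a month as 30 days (my assumption), steroids started on day *s* allow resumption no earlier than day *s* + 30, and *s* + 30 ≥ 44 when *s* ≥ 14. The first atezolizumab dose is on day 8, so steroids started between about day 14 and day 28 would push Cycle 2 past the 14-day limit. Apart from the combined transaminase and bilirubin criterion in Section 5.2.1, such Grade 2 events become DLTs only through the delay clause. The clause is not redundant.

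**Enrollment in the gap.** Section 13.3 expects 4 patients per month over the whole trial. Taking a month as 30.44 days:
- 16 days: 4 × 16 / 30.44 = 2.1 patients.
- 14 days: 4 × 14 / 30.44 = 1.8.
- 18 days: 4 × 18 / 30.44 = 2.4.

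At the first decision all of these would receive the combination. After randomization opens 1:1, about half would (2.1 / 2 ≈ 1).

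The documents give no rate for DLTs that arise only from a delay, so I attach no probability to the event.

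**The case against.** - **The count need not be incomplete.** A reader might infer that every day-28 count is incomplete by construction. The documents do not support that: Cycle 2 given on schedule closes the question at about day 29. The gap exists only while a hold for toxicity is open.
- **Late DLTs are not ignored.** The rule suspending enrollment at two DLTs has no time limit in Sections 5 and 13.3. This stands, but the rule acts only after the next cohort or randomization may have opened.
- **The committee is not blind.** Section 5 has it assess all adverse events, and Section 5.2.2 provides real-time monitoring and site notification of DLTs. In the steroid-taper cases above, a long delay is foreseeable at the review. The 4-week point is also the earliest time for each decision, not a deadline. All of this reduces the risk. None of it requires the committee to wait for a held Cycle 2, and an event that is a DLT only because of the delay cannot be counted at day 28.
- **Two patients per gap is not routine.** The accrual rate is for the whole trial, not the staggered run-in. Section 4.5 allows up to 5 business days between registration and treatment, so enrolled is not yet exposed. With staggering, earlier patients may be past day 44 when the last reaches day 28, so the open question concerns the most recently enrolled. The figure is an approximate worst case.
- **Lengthening the evaluability window is not the necessary remedy.** It would change which patients are replaced. That is a clinical rule and not one to prescribe here.

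**Conclusion.** The concern holds as a contradiction between sections with a conditional safety consequence. If a run-in patient's Cycle 2 is on hold for toxicity when a decision is taken, the DLT count may be incomplete for up to about 16 days after the window closes (14 to 18 with the dosing window). One pending event can change 1/6 to 2/6. The approximate worst case is 2 patients enrolled before the suspension rule could act. That figure rests on the whole-trial accrual rate applying during the gap and on the decision being taken as soon as the text allows.

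The documents do not support a claim that the count is always incomplete, or that late DLTs have no effect. No power, alpha or sample-size figure depends on this point. It should be corrected because following the rules as written can reopen enrollment on a count that the protocol's own definition would reverse.

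**What to change.** Reconcile Sections 5, 5.2, 5.2.2 and 13.3 (and Section 5.7, which repeats the evaluability rule) so that the DLT definition, the evaluability rule and the timing of each committee decision agree, and each decision uses a DLT count that is complete for every criterion counted toward it. The text should also settle whether a delay established after day 28 is a protocol-defined DLT for the suspension rule, and how a patient is classed who leaves the study after day 28 with Cycle 2 still on hold. Whether the review timing, the list of counted criteria or another rule changes is for the sponsor's clinical team.

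The cost is wording. If the review timing is what moves, it is up to about two weeks at a step, and only when a run-in patient's Cycle 2 is actually held for toxicity.

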5.3 General Concomitant Medication and Supportive Care Guidelines

Because there is a potential for interaction of Atezolizumab and CYT107 with other concomitantly administered drugs, the case report form must capture the concurrent use of all other drugs, over-the-counter medications, or alternative therapies. The PI should be alerted if the patient is taking any agent known to affect or with the potential for drug interactions. The study team should check a frequently updated medical reference for a list of drugs to avoid or minimize use of.

Atezolizumab General Concomitant Medication Guidelines

Concomitant therapy includes any prescription medications or over-the-counter preparations used by a patient between the 7 days preceding the baseline evaluation and

the treatment discontinuation visit.

Patients who experience infusion-associated symptoms may be treated symptomatically with acetaminophen, ibuprofen, diphenhydramine, and/or cimetidine or another H2 receptor antagonist, as per standard practice (for sites outside the United States, equivalent medications may be substituted per local practice). Serious infusion-associated events manifested by dyspnea, hypotension, wheezing, bronchospasm, tachycardia, reduced oxygen saturation, or respiratory distress should be managed with supportive therapies as clinically indicated (e.g., supplemental oxygen and β_2 -adrenergic agonists; see [Section 5.1.1](#)).

Systemic corticosteroids and TNF α inhibitors may attenuate potential beneficial immunologic effects of treatment with atezolizumab but may be administered at the discretion of the treating physician. If feasible, alternatives to corticosteroids should be considered. Premedication may be administered for Cycles ≥ 2 at the discretion of the treating physician. The use of inhaled corticosteroids and mineralocorticoids (e.g., fludrocortisone) for patients with orthostatic hypotension or adrenocortical insufficiency is allowed. Megestrol administered as appetite stimulant is acceptable while the patient is enrolled in the study.

Patients who use oral contraceptives, hormone-replacement therapy, prophylactic or therapeutic anticoagulation therapy (such as low-molecular-weight heparin or warfarin at a stable dose level) should continue their use. Males and females of reproductive potential should use highly effective means of contraception.

5.3.1 *Atezolizumab Excluded Therapies*

Any concomitant therapy intended for the treatment of cancer, whether health authority approved or experimental, is prohibited unless it is specifically included in the treatment regimen described in this protocol. This includes but is not limited to the following:

- Chemotherapy, hormonal therapy, immunotherapy, radiotherapy, investigational agents, or herbal therapy (except for maintenance therapies outlined in [Section 5.3.1](#)).
 - After Cycle 1, certain forms of radiotherapy may be considered for pain palliation if patients are deriving benefit (e.g., treatment of known bony metastases); atezolizumab administration may be suspended during radiotherapy.
- Herbal therapy intended as anticancer therapy must be discontinued ≥ 1 week before initiation of study treatment; the ingredients of many herbal medicines are not fully studied, and their use may result in unanticipated drug-drug interactions that may cause, or confound assessment of, toxicity.

Initiation or increased dose of granulocyte colony stimulating factors (e.g., granulocyte colony stimulating factor, granulocyte/macrophage colony stimulating factor, and/or pegfilgrastim) is prohibited.

Patients are not allowed to receive immunostimulatory agents, including, but not limited to, IFN- α , IFN- γ , or IL-2, during the entire study. These agents, in combination with atezolizumab, could potentially increase the risk for autoimmune conditions.

Patients should also not be receiving immunosuppressive medications, including, but not limited to, cyclophosphamide, azathioprine, methotrexate, and thalidomide. These agents could potentially alter the activity and the safety of atezolizumab.

5.3.2 Recombinant Human IL-7 (CYT107)

The excluded therapies listed above ([Section 5.3.1](#)) also apply to CYT107. Immunostimulatory and immunosuppressive agents are prohibited.

Topical corticosteroids to treat injection site reaction are allowed.

Studies performed to investigate the potential of CYT107 to inhibit or to act as a time dependent inhibitor of hepatic microsomal cytochrome P450 isozymes (see Investigator Brochure) concluded that at the concentration investigated, it is unlikely that CYT107 will be involved in drug-drug interactions and CYT107 is not expected to cause clinically significant P450 inhibition or induction. However, the case report form (CRF) must capture the concurrent use of all other drugs, over-the-counter medications, or alternative therapies including vitamins and nutritional supplements.

5.4 Duration of Therapy

In the absence of treatment delays due to AE(s), treatment may continue for *up to 2 years* or until one of the following criteria applies:

- Disease progression warranting alternative systemic therapy,

Note: Patients with radiographic progressive disease (PD) who are otherwise stable without symptomatic progression may continue Atezolizumab until the next radiographic imaging time point (within 9 weeks) to assess for possible pseudoprogression.

- Intercurrent illness that prevents further administration of treatment,
- Unacceptable AE(s),
- Patient decides to withdraw from the study,
- General or specific changes in the patient's condition render the patient unacceptable for further treatment in the judgment of the investigator,
- Patient noncompliance,
- Dosing interruption lasting >12 weeks (see [Section 6.1.1](#)),
- Pregnancy
 - All women of child-bearing potential should be instructed to contact the investigator immediately if they suspect they might be pregnant (e.g., missed or late menstrual period) at any time during study participation.
 - The investigator must immediately notify CTEP in the event of a confirmed pregnancy in a patient participating in the study.

- Termination of the study by sponsor(s), or
- The drug manufacturer can no longer provide the study agent

The reason(s) for protocol therapy discontinuation, the reason(s) for study removal, and the corresponding dates must be documented in the CRF.

All patients who tolerate the protocol regimen and with either complete tumor response (CR), partial response (PR), or stable disease (SD) will be permitted to continue treatment with atezolizumab until confirmed disease progression or for up to 2 years.

Discontinuation of treatment may be considered, at the discretion of the treating physician, for patients who have attained a confirmed CR that have been treated for at least 24 weeks with atezolizumab and had at least 2 treatments beyond the date when the initial CR was declared.

5.5 Study Treatment beyond Disease Progression

Immunotherapeutic agents such as atezolizumab may produce antitumor effects by potentiating endogenous cancer-specific immune responses. The response patterns seen with such an approach may extend beyond the typical time course of responses seen with cytotoxic agents and can manifest as a clinical response after an initial increase in tumor burden or even the appearance of new lesions.

Patients with radiographic PD who are otherwise stable without symptomatic progression may continue trial treatment as long as they meet the following criteria (following consultation with Protocol PI and/or CITN Coordinating Center):

- Investigator-assessed clinical benefit
- Tolerance of study treatment
- Absence of signs and symptoms (including worsening of laboratory values) indicating disease progression
- No decline in ECOG performance status
- Absence of rapid progression of disease or threat to vital organs
- Absence of progressive tumor at critical anatomical sites (*e.g.*, cord compression) requiring urgent alternative medical intervention

Patients should remain on the trial and continue to receive monitoring according to the Study Calendar ([Section 10](#)).

